9.5 Interim Analyses

There will not be a planned interim analysis. The DSMC will have access to periodic interim reports of safety to allow them to conduct a risk-to-benefit assessment.

10. ADMINISTRATIVE SECTION

10.1. Compliance with the Protocol and Protocol Revisions

The study must be conducted as described in the final approved protocol. Documentation of approval signed by the chairperson or designee of the EC/HA must be sent to the Sponsor's protocol manager.

All revisions (protocol amendments, administrative letters, and changes to the informed consent) must be submitted to the Sponsor's protocol manager. The investigator should not implement any deviation or change to the protocol without prior review and documented approval/favorable opinion from the EC/HA of an Amendment, except where necessary to eliminate an immediate hazard(s) to study patients.

10.2. Informed Consent

Two different PIS and CF have been developed for this trial. One for clinical trial, that is mandatory, and another for the biomarker study, that is optional.

Investigators must ensure that subjects, or, in those situations where consent cannot be given by subjects, their legally acceptable representative, are clearly and fully informed about the purpose, potential risks, and other critical issues regarding clinical studies in which they volunteer to participate. Freely given written informed consent must be obtained from every subject or, in those situations where consent cannot be given by subjects, their legally acceptable representative, prior to clinical study participation, including informed consent for any screening procedures conducted to establish subject eligibility for the study.

The rights, safety, and well-being of the study subjects are the most important considerations and should prevail over interests of science and society.

10.3. Records and Reports

An investigator is required to prepare and maintain adequate and accurate case histories designed to record all observations and other data pertinent to the investigation (e.g. medical record) on each individual treated with Ipilimumab or entered as a control in the investigation. The investigator is required to retain, in a confidential manner, the data pertinent to the study.

10.4. Good Clinical Practice

This study will be conducted in accordance with Good Clinical Practice (GCP), as defined by the International Conference on Harmonisation (ICH) and in accordance with the ethical principles underlying European Union Directive 2001/20/EC and the United States Code of Federal Regulations, Title 21, Part 50 (21CFR50).

The study will be conducted in compliance with the protocol. The protocol and any amendments and the subject informed consent will receive Institutional Review Board/Independent Ethics Committee (IRB/IEC) approval/favorable opinion prior to initiation of the study.

All potential serious breaches must be reported to the Sponsor immediately. A serious breach is a breach of the conditions and principles of GCP in connection with the study or the protocol, which is likely to affect, to a significant degree, the safety or physical or mental integrity of the subjects of the study or the scientific value of the study.

Study personnel involved in conducting this study will be qualified by education, training, and experience to perform their respective task(s). This study will not use the services of study personnel where sanctions have been invoked or where there has been scientific misconduct or fraud (eg, loss of medical licensure, debarment).

Systems with procedures that ensure the quality of every aspect of the study will be implemented.

10.5. Institutional Review Board/Independent Ethics Committee (IRB/IEC)

Before study initiation, the investigator must have written and dated approval/favorable opinion from the IRB/IEC for the protocol, consent form, subject recruitment materials/process (eg, advertisements), and any other written information to be provided to subjects. The investigator should also provide the IRB/IEC with a copy of the SMPCor product labeling, information to be provided to subjects and any updates.

The investigator should provide the IRB/IEC with reports, updates and other information (eg, expedited safety reports, amendments, and administrative letters) according to regulatory requirements or institution procedures

10.6. Records Retention

The investigator must retain Ipilimumab disposition records, source documents, and case histories designed to record all observations and other data pertinent to the investigation (e.g. medical record) for the maximum period required by applicable regulations and guidelines, or Institution procedures.

If the investigator withdraws from the study (e.g., relocation, retirement), the records shall be transferred to a mutually agreed upon designee (e.g., another investigator, IRB). Documentation of such transfer must be provided to the Sponsor.

11. REFERENCES

APPENDIX 1

KARNOFSKY PERFORMANCE STATUS SCALE

Value	Level of functional capacity	Definition
100	Normal, no complaints, no evidence of disease	Able to carry on normal activity and to work; no special care needed
90	Able to carry on normal activity, minor signs or symptoms of disease	
80	Normal activity with effort, some signs or symptoms of disease	
70	Cares for self, unable to carry on normal activity or to do active work	Unable to work; able to live at home and care for most personal needs; various degrees of assistance needed
60	Requires occasional assistance, but is able to care for most needs	
50	Requires considerable assistance and frequent medical care	
40	Disabled, requires special care and assistance	Unable to care for self; requires equivalent of institutional or hospital care; disease may be progressing rapidly
30	Severely disabled, hospitalization is indicated although death is not imminent	
20	Hospitalization is necessary, very sick, active supportive treatment necessary	
10	Moribund, fatal processes progressing rapidly	
0	Dead	

The Karnofsky score runs from 100 to 0, where 100 is "perfect" health and 0 is death.

References:

APPENDIX 2

BARTHEL INDEX OF ACTIVITIES OF DAILY LIVING

Instructions: Choose the scoring point for the statement that most closely corresponds to the patient's current level of ability for each of the following 10 items. Record actual, not potential, functioning. Information can be obtained from the patient's self-report, from a separate party who is familiar with the patient's abilities (such as a relative), or from observation. Refer to the Guidelines section on the following page for detailed information on scoring and interpretation.

Bowels

0 = incontinent (or needs to be given enemata)

1 = occasional accident (once/week)

2 = continent

Patient's Score:

Bladder

0 = incontinent, or catheterized and unable to manage

1 = occasional accident (max. once per 24 hours)

2 = continent (for over 7 days)

Patient's Score:

Grooming

0 = needs help with personal care

1 = independent face/hair/teeth/shaving (implements provided)

Patient's Score:

Toilet use

0 = dependent

1 = needs some help, but can do something alone

2 = independent (on and off, dressing, wiping)

Patient's Score:

Feeding

0 = unable

1 = needs help cutting, spreading butter, etc.

2 = independent (food provided within reach)

Patient's Score:

GRAY-B Study (GEM 1202). V1.0 (28 Nov 2013)

Transfer

0 = unable – no sitting balance

1 = major help (one or two people, physical), can sit

2 = minor help (verbal or physical)

3 = independent

Patient's Score:

Mobility

0 = immobile

1 = wheelchair independent, including corners, etc.

2 = walks with help of one person (verbal or physical)

3 = independent (but may use any aid, e.g., stick)

Patient's Score:

Dressing

0 = dependent

1 = needs help, but can do about half unaided

2 = independent (including buttons, zips, laces, etc.)

Patient's Score:

Stairs

0 = unable

1 = needs help (verbal, physical, carrying aid)

2 = independent up and down

Patient's Score:

Bathing

0 = dependent

1 = independent (or in shower)

Patient's Score:

Total Score:

Scoring:

Sum the patient's scores for each item. Total possible scores range from 0 – 20, with lower scores indicating increased disability. If used to measure improvement after rehabilitation, changes of more than two points in the total score reflect a probable genuine change, and change on one item from fully dependent to independent is also likely to be reliable.

Guidelines for the Barthel Index of Activities of Daily Living

General

- The Index should be used as a record of what a patient *does*, NOT as a record of what a patient *could do*.
- The main aim is to establish degree of independence from any help, physical or verbal, however minor and for whatever reason.
- The need for supervision renders the patient not independent.
- A patient's performance should be established using the best available evidence. Asking the patient, friends/relatives, and nurses will be the usual source, but direct observation and common sense are also important. However, direct testing is not needed.
- Usually the performance over the preceding 24 – 48 hours is important, but occasionally longer periods will be relevant.
- Unconscious patients should score '0' throughout, even if not yet incontinent.
- Middle categories imply that the patient supplies over 50% of the effort.
- Use of aids to be independent is allowed.

Bowels (preceding week)

- If needs enema from nurse, then 'incontinent.'
- 'Occasional' = once a week.

Bladder (preceding week)

- 'Occasional' = less than once a day.
- A catheterized patient who can completely manage the catheter alone is registered as 'continent.'

Grooming (preceding 24 – 48 hours)

- Refers to personal hygiene: doing teeth, fitting false teeth, doing hair, shaving, washing face. Implements can be provided by helper.

Toilet use

- Should be able to reach toilet/commode, undress sufficiently, clean self, dress, and leave.
- 'With help' = can wipe self and do some other of above.

Feeding

- Able to eat any normal food (not only soft food). Food cooked and served by others, but not cut up.

GRAY-B Study (GEM 1202). V1.0 (28 Nov 2013)

- 'Help' = food cut up, patient feeds self.

Transfer

- From bed to chair and back.
- 'Dependent' = NO sitting balance (unable to sit); two people to lift.
- 'Major help' = one strong/skilled, or two normal people. Can sit up.
- 'Minor help' = one person easily, OR needs any supervision for safety.

Mobility

- Refers to mobility about house or ward, indoors. May use aid. If in wheelchair, must negotiate corners/doors unaided.
- 'Help' = by one untrained person, including supervision/moral support.

Dressing

- Should be able to select and put on all clothes, which may be adapted.
- 'Half' = help with buttons, zips, etc. (*check!*), but can put on some garments alone.

Stairs

- Must carry any walking aid used to be independent.

Bathing

- Usually the most difficult activity.
- Must get in and out unsupervised, and wash self.
- Independent in shower = 'independent' if unsupervised/unaided.

References:

1.2. BASELINE CHARACTERISTICS

The database was closed on XX-XX-XXXX and based on the population of **XX patients** included / treated in the study, the baseline characteristics are presented:

Table 4. Baseline characteristics (I)

	N	Mean (SD)	Median (Min-Max)
Age (years)			
Karnofsky functional status (0-100)			
Barthel index (0-20)			

Table 5. Baseline characteristics (II)

		N (%)
Sex	Male	
	Female	
	Total	
KPS	70-80	
	90-100	
	Not specified	
	Total	
Barthel Index	<15	
	15-20	
	Total	
Status B-Raf (Current Melanoma)	Mutated	
	Native	
	Not specified	
	Total	
N° of lines of previous treatment	0	
	1	
	> 1	
	Total	
Status B-Raf (Previous Melanoma)	Mutated	
	Native	
	Not specified	
	Total	
Brain M1	Multiple	
	Single	
	Not specified	
	Total	
No. of organs with metastatic disease	1	
	2	
	3	
	4	
	5	
	Total	
No. of organs with metastatic disease	≤2	
	> 2	
	Total	
Brain metastases	Yes	
	Total	
Pulmonary metastases	No	
	Yes	
	Total	
Hepatic metastases	No	
	Yes	
	Total	

Metastasis Skin	No	
	Yes	
	Total	
Gastrointestinal metastases	No	
	Yes	
	Total	
Locoregional lymph node metastases	No	
	Yes	
	Total	
Distant lymph node metastases	No	
	Yes	
	Total	

1:% with respect to *included patients* with available data.

Table 6. Use of previous BRAF inhibitors

		N (% ¹)
Use of previous BRAF inhibitors	No	
	Yes	
	Total	
Type of treatment lines BRAF inhibitor	BRAFi	
	BRAFi + MEKi	
	Vemurafenib + Pembrolizumab	
	Total	

1:% with respect to *included patients* with available data.

Table 7. Corticosteroids at baseline and / or cycle 1

		N (% ¹)
Corticosteroids at baseline and / or C1	No	
	Yes	
	Total	

1:% with respect to *included patients* with available data.

Table 8. Mean daily dose (dexamethasone reference)

	N	Mean (SD)	Median (Min-Max)
Mean daily dose (Dexamethasone)			

1:% with respect to the *patients included* with available data (patients who received corticosteroids and for whom the dose)

Table 9.: Hematology

	N	Mean (SD)	Median (Min-Max)
Leukocytes x10 ³ / uL			
Eosinophils			
Baseline laboratory tests Basophils			
Monocytes			
Neutrophils			
Lymphocytes			
Neutrophils Total x10 ³ / uL			
Eosinophils Total x10 ³ / uL			
Basophils Total x10 ³ / uL			
Total Monocytes x10 ³ / uL			
Total Lymphocytes x10 ³ / uL			
Hemoglobin g / dl			
Platelets x10 ³ / uL			
Neutrophil / Lymphocyte Ratio			

The mean baseline LDH value was 420.3 U / L. Baseline blood tests

Table 10.: Biochemistry

	N	Mean (SD)	Median (Min-Max)
Creatinine (mg / dl)			
Creatinine Clearance (ml / min)			
SGOT / AST (U / L)			
SGTP / ALT (U / L)			
Total Bilirubin (mg / dL)			
CRP			
Ureic Nitrogen or Urea (mg / dL)			
Glucose (mg / dL)			
Sodium (mmol / L)			
Chloride (mmol / L)			
Bicarbonate (mmol / L)			
Baseline LDH (U / L)			

Table 11. LDH categorized

		N (% ¹)
Value of LDH > ULN	No	
	Yes	
	Total	
LDH value > 1.5 * ULN	No	
	Yes	
	Total	

1:% with respect to *included patients* with available data.

Table 12. Baseline analysis: Endocrine

	N	Mean (SD)	Median (Min-Max)
Cortisol (ug / dl)			
ACTH (pg / mL)			
T4 (ug / mL)			
T3 (ug / mL)			
TSH (uIU / mL)			
Prolactin (ng / ml)			

1.3. TREATMENT EXPOSURE

Table 13. IPI treatment (I)

		N (%)
Total number of Ipilimumab cycles	1	
	2	
	3	
	4	
	Total	
	Total	
number of omissions	0	
	1	
	2	
	3	
	Total	
	Total	
number of reductions	0	
	1	
	2	
	3	
	4	
	Total	
number of delays	0	
	1	
	2	
	3	
	Total	
	Total	

1:% with respect to *patients included* with available data

Table 14. RDT treatment (I)

		N (%)
Premature end of RDT	No	
	Yes	
	Total	
		N (%)
Reason for interruption of RDT treatment		

1:% with respect to *patients included* with available data

Table 15. Duration of RDT

	N	Mean (SD)	Median (Min-Max)
Duration of RDT			

Table 16. Patients with no end date of RDT

Patient code	Duration RDT	EndRDT	date ofStart date of RDT
1			

1.4. Screening of all patients

median follow-up for *the patient population treated, n = XX*, was XXmonths.

Table 17. Time tracking all patients

	N	Mean (SD)	median (Me n-Max)
Follow-up time (months from 1st cycle of Ipilimumab)			

1.5. EFFECTIVENESS ANALYSIS

Following the protocol, the population of was used for the efficacy analysis **evaluable patients: n = XX (see section 1.1)**

1.5.1. OVERALL SURVIVAL (Evaluable)

Survival Overall (OS) is presented for evaluable patients (n = XX). The estimated overall survival at one year (calculated using Kaplan-Meier) was X% (with a 95% CI: XX%) with a median OS of X months (95% CI XX months).

Table 18. Overall survival (evaluable)

Estimated overall survival	N events	N at risk	% of patients without death	95% CI	% with death
at 6 months					
to 12 months					
	N (%)	Median	Min-Max	Standard Error	95% Confidence interval
Overall survival Estimated					

Table 19. Overall survival: Events and OS at 1 year (Evaluable)

		N (%; 95% CI)
Overall survival	Live	
	Exitus	
	Total	
OS at 1 year (crude)	No	
	Yes	
	No follow-up at 1 year (or death)	
OS at 1 year (gross) (excluding patients with follow-up <1 year and without previous death)	Total	
	No	
	Yes	
	Total	

Figure 1. Estimated overall survival (Evaluable)

Table 20. Time to Exitus (only in patients with death)

	N	Mean (SD)	Median (Min-Max)
Time to Exitus			

Table 21. Reasons for leaving the study (evaluable)

	N (%)
Reason Exitus Progression of the disease	

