Study Schema: Drugs / Doses / Length of Treatment)	
 • Ipilimumab 3mg/Kg iv q 3 weeks for 4 cycles • WBRT 30 Gy in 10 fractions (or radiobiological equivalent schedule, after Sponsor approval), starting between C1D2 and C2D1
Study Objectives: Primary: Secondary:	
Primary Objective
 
 • Efficacy - Primary endpoint: 1-year survival rate 
Secondary Objectives
 
 • Efficacy – Endpoints: 
 ○ Progression-Free survival-PFS (median, 6-month PFS rate) 
 ▪ Intracranial PFS (median, 6-month PFS rate)

	
 ▪ Extracranial PFS (median, 6-month PFS rate) 
 ○ Overall survival (median) ○ Response rate: (global, intracranial, extracranial) (“Immune-related response criteria”) ● Safety: Adverse Event rates ● Feasibility: dose delays/reductions, treatment exposure
Study Design:	Multicenter, single arm, phase 2 clinical study on the combination of radiation therapy and ipilimumab
Accrual Goal: (Total number of patients)	56 patients treated 66 included
Accrual Rate: (Number of patients expected per month)	3 to 4 patients per month
FPFV: LPFV: Follow Up: (dd-mm-yy)	03/2014 10/2015 10/2016
Correlative Studies: (PK/PD, etc.)	
Exploratory Objectives.
 
 ○ Potential baseline predictors of efficacy (in tumor tissue and peripheral blood) 
Potential early surrogates for response: inpatient variation of quantitative apparent diffusion coefficients of serial diffusion-weighted magnetic resonance imaging

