2.2 Secondary Objectives

- Efficacy – Endpoints:
 - Progression-Free survival-PFS (median, 6-month PFS rate)
 - Intracranial PFS (median, 6-month PFS rate)
 - Extracranial PFS (median, 6-month PFS rate)
 - Overall survival (median)
 - Response rate: (global, intracranial, extracranial) (“Immune-related response criteria”)
- Safety: Adverse Event rates
- Feasibility: dose delays/reductions, treatment exposure

2.3. Exploratory Objectives.

- Potential baseline predictors of efficacy (in tumour tissue and peripheral blood – see 6.4.3.)
- Potential early surrogates for response: inpatient variation of quantitative apparent diffusion coefficients of serial diffusion-weighted magnetic resonance imaging

⁶⁸ Hodi FS, O'Day SJ, McDermott DF, et al. Improved survival with ipilimumab in patients with metastatic melanoma. *N Engl J Med.* 2010 Aug 19;363(8):711-23.

⁶⁹ http://www.ema.europa.eu/docs/en_GB/document_library/EPAR_-_Product_Information/human/002213/WC500109299.pdf

3 **STUDY DESIGN**

This is a non-controlled, single stage, multicenter phase 2 clinical study. A total of 56 evaluable patients will be treated in this study.

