9. STATISTICAL METHODOLOGY

9.1. Sample size.

The primary endpoint in this study is the 1-year actual survival rate. A one-stage Fleming design has been adopted. Assuming a historical 1-year survival rate of 20% (with radiation therapy + best supportive care) for the selected population, a sample size of 56 evaluable patients would be needed to show that the addition of ipilimumab to radiotherapy generates a 1-year survival rate of 35%, reaching 80% power at the 0.05 significance level.

A total of 56 evaluable patients would need to be included. In case that at least 17 out of these 56 evaluable patients would survive for at least one year, the conclusion of the trial would be that the higher 1-year survival rate of 35% is more likely for the combination than the historical 20% survival rate.

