9.2 Populations for Analyses

- Enrolled Subjects: All subjects who signed and informed consent form and were registered.
- Treated Subjects (Safety Population): Includes all subjects in the study who receive at least one dose of ipilimumab. Unless otherwise indicated, analyses of drug exposure and safety will be performed on this population as treated.

- Evaluable Subjects: Includes all subjects who received at least 1 dose of ipilimumab and the full WBRT therapy.
- Biomarker Subjects: Includes all treated subjects with at least baseline biomarker studies.

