9.4.2 Efficacy Analyses

9.4.2.1 *Methods for Time to Event Primary Endpoint*

The yearly rate of survivors will be the actual proportion of patients alive after 1 year of the first administration of ipilimumab.

9.4.2.2 *Methods for Time to Event Secondary Endpoints*

The overall survival and event-free survival probabilities will be estimated and plotted using the Kaplan-Meier product-limit method.

Additionally, 1 and 2 year rates will be also based upon Kaplan-Meier estimates along with their corresponding log-log transformed 95% confidence intervals.

The progression-free survival probabilities will also be estimated and plotted using the Kaplan-Meier product-limit method. Duration of response, duration of stable disease, and overall survival in subjects with brain metastasis will also be described using these same Kaplan-Meier methods.

A differential analysis will be done with intracranial and extracranial disease.

9.4.2.3 *Methods for Proportion Based Rates Secondary Endpoints*

For BORR and DCR, descriptive summary statistics (e.g., total number of patients, number and percent responders, 95% confidence interval) will be used. An exact two-sided 95% CI for these rates will be computed. A differential analysis will be done with intracranial and extracranial disease.

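### The success rule of 17 out of 56 has no counterpart for any other number of evaluable patients, although the realised number can differ from 56

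*SAP*

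**What the plan says.** **Decision rule.** Protocol 9.1, repeated in the statistics row of the synopsis, assumes a historical one-year survival rate of 20%, targets 35% with 80% power at the 0.05 level, and asks for 56 evaluable patients. The criterion is "In case that at least 17 out of these 56 evaluable patients would survive for at least one year".

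**Estimator.** Protocol 9.4.2.1: "The yearly rate of survivors will be the actual proportion of patients alive after 1 year of the first administration of ipilimumab". Kaplan-Meier rates appear in 9.4.2.2, under the secondary endpoints.

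**Who counts.** Protocol 9.2 defines evaluable subjects: "Includes all subjects who received at least 1 dose of ipilimumab and the full WBRT therapy". Section 3 (Study Design) says "A total of 56 evaluable patients will be treated in this study", while the accrual row of the synopsis says "56 patients treated 66 included".

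**SAP.** Section 1.5 uses "evaluable patients: n = XX (see section 1.1"), and 1.5.1 reports "Survival Overall (OS) is presented for evaluable patients (n = XX). The estimated overall survival at one year (calculated using Kaplan-Meier) was X". Table 19 adds two crude one-year rates: one with a separate category for patients without one-year follow-up, and one that leaves out patients who were followed for less than a year and had not died. Table 14 plans a count under "Premature end of RDT". The visible SAP restates neither the 17 of 56 rule nor a test against 20%.

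**The concern.** The trial has one decision rule, and it is written for one denominator. Evaluable status is known only after radiotherapy has been given. Treating 56 patients and having 56 evaluable patients are the same thing only if every treated patient completes WBRT, and the SAP itself provides for some who do not. If the analysis arrives with another number, the team must either keep 17, and miss the stated error rate or power, or choose a cut-off once the data are in hand.

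The definition has a second consequence. A patient who dies before completing WBRT leaves the evaluable set, which raises the one-year rate among those who remain.

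**Working it through.** **1. The plan's own figure.** Inputs from protocol 9.1: p0 = 0.20, p1 = 0.35, N = 56, cut-off 17. With X binomial(56, p):

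- alpha = P(X ≥ 17 | 0.20) = 0.0432
- power = P(X ≥ 17 | 0.35) = 0.8064

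Sidedness is not stated. The smallest exact design at one-sided 0.05 with at least 80% power is N = 56 with cut-off 17; at one-sided 0.025 it would be N = 72 with cut-off 22. The rule is therefore an exact one-sided 5% test and is reproduced.

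**2. Other N.** The exact cut-off is the smallest r with P(X ≥ r | N, 0.20) ≤ 0.05.

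| N | alpha, keep 17 | power, keep 17 | exact cut-off | its alpha | its power |
|---|---|---|---|---|---|
| 50 | 1.44% | 61.1% | 16 | 3.08% | 72.0% |
| 52 | 2.15% | 68.5% | 16 | 4.36% | 78.2% |
| 53 | 2.59% | 71.9% | 17 | 2.59% | 71.9% |
| 56 | 4.32% | 80.6% | 17 | 4.32% | 80.6% |
| 57 | 5.05% | 83.1% | 18 | 2.61% | 74.9% |
| 58 | 5.85% | 85.3% | 18 | 3.10% | 77.8% |

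Over the wider range the exact cut-off is 15 for N = 45-48, 16 for 49-52, 17 for 53-56 and 18 for 57-61.

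**3. Power when 56 or 58 are treated.** The documents give no WBRT completion rate, so it is assumed here, and assumed unrelated to survival. Evaluable N is then binomial(treated, completion), and power is averaged over it.

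| Treated | Completion | keep 17 | cut-off for realised N |
|---|---|---|---|
| 56 | 95% | 72% | 75% |
| 56 | 90% | 62% | 73% |
| 56 | 85% | 51% | 71% |
| 58 | 95% | 78% | 77% |
| 58 | 90% | 69% | 75% |
| 58 | 85% | 58% | 73% |

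**4. If early death is the only reason for incomplete WBRT.** Assume exponential survival with a true one-year rate of 20% in all treated patients. WBRT may start from the day after the first ipilimumab dose up to the second dose three weeks later and takes ten daily fractions, so it ends at about day 13 at the earliest and about day 35 at the latest.

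- Dead by day d: 1 − 0.20^(d/365) = 5.6% at day 13 and 14.3% at day 35.
- One-year rate among those remaining: 0.20/(1 − 0.056) = 21.2%, and 0.20/(1 − 0.143) = 23.3%.
- P(X ≥ 17 of 56 evaluable) at those rates: 6.9% and 14.0%.
- Test at the realised evaluable N, 56 treated: 5.5% and 10.8%.
- Exact test in all treated: 4.3% at N = 56 and 3.1% at N = 58.

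**5. Table 19, excluding row.** With dropout probability q independent of death, the row estimates S(1−q) / [S(1−q) + (1−q)(1−S) + q·d], where d is the chance that a patient due to drop out dies first. For S = 0.35, q = 0.05 and dropout uniform between 0.1 and 1 year (assumed), d = 0.418, so 0.3325/(0.3325 + 0.6175 + 0.0209) = 34.2%.

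**The case against.** The strongest reply is that the target is fixed: 9.1, section 3 and the statistics row of the synopsis all say 56 evaluable, and only the accrual row says treated. That stands. What can vary is the realised number, and 17 remains the exact cut-off anywhere from 53 to 56.

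It can also be said that a realised-N test is not always better. That stands too. With 58 treated and about 95% completion or more, a fixed 17 has slightly more power (78% against 77% at 95%; 83% against 77% at 98%). If early death is the only cause of incomplete WBRT and 56 are treated, a fixed 17 keeps alpha at 4.3%, because those deaths count as failures whether or not they are in the denominator. This is why the realised-N test should not stand without an all-treated test.

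Some stronger readings are tempting, but the documents do not support them:

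- *That 58 patients were treated, so 17 is the wrong cut-off.* Two placeholder rows in SAP Table 51 keep counts of 49 + 9 and 43 + 15, and 58 is the only denominator that fits their percentages. They sit in a safety table of treated patients whose other cells are blank. If they come from this trial, 58 is at most an upper bound on evaluable N, and alpha exceeds 5% only if 57 or 58 are evaluable.
- *That Table 19 is biased downward whatever happens.* This needs independent censoring and at least one patient lost alive before one year; if sicker patients are lost, the direction can reverse. The row is labelled and sits beside Kaplan-Meier.
- *That unknown one-year status leaves the rule undefined.* The study closes 18 months after the last first dose (section 3), and survival is checked at least every 12 weeks (9.3.1), so unknown status should be rare. Under 9.1 and 9.2 such a patient stays in the denominator and is not a documented survivor.
- *That the SAP has replaced the primary analysis or dropped the test.* Protocol 9.4.2.1 still governs, and SAP section 1.1 was not available to check.

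**Conclusion.** The concern holds as a minor one. The rule is right at its planned N, and no visible text carries it to another. If 17 is kept, the one-sided error rate passes 5% only slightly (5.05% at N = 57, 5.85% at N = 58), while power falls faster on the other side (68.5% at N = 52, 61.1% at N = 50). With exactly 56 treated, 95% or 90% completion leaves 72% or 62% power; those figures assume that completion is unrelated to survival. If completion instead fails only through early death, the evaluable analysis is lenient relative to 20% in all treated patients: about 6.9 to 14.0% for 17 of 56 evaluable, and 5.5 to 10.8% for the realised-N test, under exponential survival. The Table 19 issue is small and conditional.

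**What to change.** 1. In protocol 9.1 and SAP 1.5.1, label the observed proportion in evaluable patients as primary and test it against 20% with an exact one-sided 5% binomial test at the realised N. Print the cut-offs: 15 for 45-48, 16 for 49-52, 17 for 53-56, 18 for 57-61. Say that the test is one-sided.
2. Report the same exact test in all treated patients beside it. State in advance that success in evaluable patients will not be claimed without qualification if the two disagree.
3. Reconcile the synopsis accrual row with section 3 and 9.1 on whether 56 means treated or evaluable.
4. Mark the Table 19 excluding row as descriptive, or drop it, and keep Kaplan-Meier as the supportive estimate. Write down that a patient with unknown one-year status stays in the denominator and is not counted as alive.

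The cost is wording; no data or visits are added, and the cut-off usually moves by one. The downside is slightly less power than a fixed 17 if 58 are treated and about 95% or more complete WBRT.
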